#### **6.2.9. Visit 12 - End of Study (Day 504 +/- 7 days)**

The following procedures will be conducted at the listed visits in chronological order:

- Cough VAS, KBILD Questionnaire and LCQ
- AEs and concomitant medications since previous visit
- Modified PE (Lungs and CV body systems only)
- Weight
- Vital signs
- SaO2
- Spirometry and DLCO
- Blood samples for laboratory tests (Chemistry including AST and ALT, Hematology, Biomarkers (CA19-9 and CA-125 only))
- Urinalysis
- Urinary pregnancy test (FOCBP only)
- End of Treatment for Part B form completion
- Informed Consent for continued treatment until enrollment in the AP01-005 Rollover study (Patients waiting approval of AP01-005 at their site only.)

#### **6.2.10 Safety Monitoring Visits for Patients Awaiting Site Approval to Enroll in AP01-005 Only (Day 588 +/- 7 days)**

- Spirometry
- AST and ALT
- Saturated Oxygen (SaO2)
- Urinary pregnancy test for females of childbearing potential (FOCBP) only

Avalyn Pharma, Inc.  
AP01-002

Protocol v2.1  
12 OCT 2020

- Abnormalities on chest and skin exam
- Vitals
- AEs and concomitant medications since previous visit

#### **6.2.11 Follow-up Visit for Patients NOT Enrolling in AP01-005 (28 days +/- 7 days after the Visit 12 - End of Study visit)**

Follow-up visits will occur 28 days after the End of Study visit for Part B. The following procedures will be conducted in chronological order:

- Cough VAS, KBILD Questionnaire and LCQ
- AEs and concomitant medications since previous visit
- Modified PE (Lungs and CV body systems only)
- Vital signs
- SaO2
- Spirometry and DLCO
- Blood samples for laboratory tests (Chemistry including AST and ALT, Hematology, Biomarkers (CA19-9 and CA-125 only))
- Urinalysis
- End of Study form completion

Patients may experience AEs that necessitate an unscheduled visit. There may also be situations in which the investigator asks a patient to report for an unscheduled visit following the report of an AE or a significant decrease in FVC during home spirometry readings. Additional examinations may be conducted at these visits as necessary to ensure the safety and well-being of patients during the study. Electronic case report forms (eCRFs) should be completed for each unscheduled visit.

Avalyn Pharma, Inc.  
AP01-002

Protocol V2.1  
12 OCT2020

**Table 5: Study Schedule for Part A**

	Study Phase – Part A							
	Screening	Baseline	Treatment					
	Visit 1	2	3	4	5	6	7	8
Day	-30 to -1	1	28	56	84	112	140	168
Window (Days)	NA	NA	+/- 3	+/- 3	+/- 3	+/- 3	+/- 3	+/- 3
Informed Consent	X							
Eligibility Assessments	X	X						
Assessment of IPF Diagnosis	X							
Demographics	X							
Medical History	X							
Physical Exam 	X	X	X	X	X	X	X	X
Height  , Weight	X				X			X
Vital Signs	X	X	X	X	X	X	X	X
ECG	X							
Laboratory Tests 	X	X	X	X	X	X	X	X
Urinalysis	X	X	X	X	X	X	X	X
Urinary Pregnancy Test 	X	X	X	X	X	X	X	X
Spirometry and D LCO	X	X	X	X	X	X	X	X
SaO 2	X		X	X	X	X	X	X
LCM  and diary dispensation	X				X			X
Cough VAS, KBILD Questionnaire and LCQ		X	X	X	X	X	X	X
HRCT 		X						X
Pre-dose Spirometry		X						
Pre-dose SaO 2		X						
Randomization		X						
Study Material Training		X						
Study Drug Administration First Dose		X						
Post-dose Spirometry (≤ 10 min post-dose)		X						
Post-dose SaO 2		X						
Study Material Dispensation		X	X	X	X	X	X	X 
Home Spirometer Training and Dispensation		X						
Concomitant Medications	X	X	X	X	X	X	X	X
Adverse Events		X	X	X	X	X	X	X
End of Treatment/Study Form								X

Avalyn Pharma, Inc.  
AP01-002

Protocol V2.1  
12 OCT2020

**Table 6: Study Schedule for Part B**

Visit	Study Phase – Part B				Follow-up 	Safety Visit 
	Treatment					
	9	10	11	12 		
Day	252	336	420	504 End of Study	28 days after End of Study	588
Window (Days)	+/- 7	+/- 7	+/- 7	+/- 7	+/- 7	+/- 7
Cough VAS, KBILD and LCQ	X	X	X	X	X	
Physical Exam 	X	X	X	X	X	X
Weight		X		X		
Vital Signs	X	X	X	X	X	X
Laboratory Tests 	X	X	X	X	X	X
Urinalysis	X	X	X	X	X	
Urinary Pregnancy Test 	X	X	X	X		X
Spirometry and D LCO	X	X	X	X	X	X 
Saturated Oxygen	X	X	X	X	X	X
Study Material Dispensation	X	X	X	X 		X
Concomitant Medications	X	X	X	X	X	X
Adverse Events	X	X	X	X	X	X
End of Treatment/Study Form				X	X	
Informed Consent to continue AP01 until enrollment in AP01-005 				X		

**Notes for Tables 5 and 6:**

1. Follow-up visit will occur 28 days after the End of Study visit in Part B of the study.
2. A complete physical exam will be performed at Screening and Baseline visits. A modified physical exam including the patient's lungs and cardiovascular body systems will be performed at all other visits. For Safety Visits, only chest and skin exam are required.
3. Height is collected at the Screening visit only.
4. Blood samples for laboratory tests include: Chemistry (including AST and ALT), Hematology and Biomarkers (Blood samples for biomarkers will not be collected at Screening.) For Safety Visits, only AST and ALT are required.
5. Females of childbearing potential are required to take a urinary pregnancy test at each visit except the Follow-up visit.
6. Patients that pass screening and are scheduled to be randomized will receive a LCM to be worn for 24 hours and returned to the site at the Baseline visit. LCM will be worn for 24 hours at Visits 5 and 8. A paper diary will also be dispensed to the patient to record activities during the 24-hour period.
7. HRCT scans will be performed at Visits 2 and 8. The Baseline HRCT may be skipped if the HRCT for eligibility was performed less than 1 month prior to the Baseline visit.
8. Study material dispensation will occur at Visit 8 for those patients participating in Part B of the study.
9. Patients will be assessed for eligibility to participate in AP01-005 at EOS/Visit 12. Those enrolling in AP01-005 will use EOS/Visit 12 as their AP01-005 Baseline visit.
10. Patients enrolling in AP01-005 will not participate in the Follow-up visit.
11. Patients awaiting site approval of AP01-005 only.

Avalyn Pharma, Inc.  
AP01-002

Protocol V2.1  
12 OCT2020

12. For Safety Visits, DLco not required.
13. Study Material Dispensation only for patients continuing AP01 at Visit 12.

**Table 7: Patient At-Home Assessments**

DAILY: Patients will administer AP01 50 once daily or 100 mg twice daily
WEEKLY: Patients will perform home spirometry readings on the same day each week at approximately the same time of day (+/- 2 hours) during Part A and Part B of the study

Avalyn Pharma, Inc.  
AP01-002

Protocol V2.1  
12 OCT2020

## **7. ASSESSMENTS**

### **7.1. Background Assessments**

#### **7.1.1. Demographic/Medical History**

Information relating to the patient's sex, age, race, height, and weight will be recorded at Screening on the appropriate eCRF page. Medical history of each patient will be collected at Screening and recorded on the appropriate eCRF page.

### **7.2. Efficacy Assessments**

#### **7.2.1. FVC**

Pre and post-dose spirometry will be conducted the day of first dose. The post-dose spirometry reading should be performed  $\leq 10$  minutes after completion of the AP01 dose. Spirometry will be conducted at approximately the same time each visit (within 60 minutes of Day 1 pre-dose spirometry measurement) with the patient in seated position. The test will be performed to American Thoracic Society/European Respiratory Society (ATS/ERS) guidelines. On days of clinic visits (including the screening visit), patients must refrain from strenuous activity at least 12 hours prior to pulmonary function testing. FVC % predicted will be calculated using the ERS Global Lung Function Initiative 2012 equations as outlined in the clinical study manual.

#### **7.2.2. Leicester Cough Monitor**

The LCM is an audio-based cough detection device that allows sounds to be reconstructed and measured as cough events. Patients that pass all of the screening criteria and will be randomized in the study will be provided with a cough monitor to wear for a 24-hour period prior to coming in for their Baseline visit. This will be used as their baseline reading. The LCM and mailing materials will also be dispensed at Visits 5 and 8. Patients will wear for a 24-hour period, fill out the cough monitor paper diary and when complete, mail the LCM and diary back using the mailing materials provided. Further details regarding LCM dispensation and return will be outlined in the clinical study manual.

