The DSMB for this study met on 12 OCT 2020 to review preliminary dose comparison data. It was determined that the 100 mg twice daily dose showed a trend for amelioration of FVC loss and recommended all patients in Part B be treated with the 100 mg twice daily dose. Therefore, all patients who participate in Part B after the implementation of this amendment will be treated with the 100 mg twice daily dose. Any patients already participating in Part B on the 50 mg once daily dose will be converted to the 100 mg twice daily dose regimen. Patients will have monthly telephone assessments and quarterly in-clinic assessments. All patients that complete the study visits through Part B will have the option to continue receiving AP01 by enrolling or planning to enroll in the AP01-005 study or to stop dosing after the EOS/Visit 12 and return for a Follow-up visit, 28 days after their End of Study visit.

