#### **6.2.6. Visit 8 - End of Part A (Day 168 +/- 3 days)**

The following procedures will be conducted at the listed visits in chronological order:

- Cough VAS, KBILD Questionnaire and LCQ
- AEs and concomitant medications since previous visit
- Modified PE (Lungs and CV body systems only)
- Weight
- Vital signs
- SaO2
- Spirometry and DLCO
- Blood samples for laboratory tests (Chemistry including AST and ALT, Hematology, Biomarkers (CA19-9 and CA-125 only))
- Urinalysis
- Urinary pregnancy test (FOCBP only)
- HRCT
- LCM dispensation
- End of Treatment form for Part A completion
- Study material dispensation (3-month supply for patients participating in Part B only)

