#### **6.2.7. Monthly Calls to Patient**

During Part B, the site will conduct a monthly call to the patient between visits to assess tolerability, study drug compliance, AEs, concomitant medications, status of the LCM return (when applicable) and use of the home spirometer.

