6.4. Visit Windows

All data collected during study follow-up will be displayed and analyzed according to the actual visit data in the eCRF with the exception of early termination visits. Early termination visits will be mapped to the closest study visit, or analyzed according to the actual visit date, when possible.

The study assessments are summarized in Table 1 and Table 2 of the clinical study protocol. All information required by the protocol must be recorded on the source documents. The study schedule must be followed. However, under special conditions (e.g., holidays, weekends), a window of +/- 3 days is permissible for study procedures as long as the proper order of procedures and assessments is maintained. In Phase 2, a window of +/- 7 days is permissible. These windows are not applicable during the baseline period. Out-of-window data will be retained in the tables, listings, and figures. For the Part A interim analysis, Visit 8 will include data collected up to 36 weeks for HRCT and 28 weeks for all other variables.

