and when complete, mail the LCM and diary back using the mailing materials provided. Further details regarding LCM dispensation and return will be outlined in the clinical study manual.

The following statistics for cough frequency (coughs/hour) as measured by LCM will be calculated and summarized separately for 24 hours and for awake time by treatment group and displayed in a table:

- Summary statistics of the cough frequency (coughs/hour) as measured by LCM at Baseline and at Visits 5 and 8 (Week 12 and 24)
- Summary statistics of the cough frequency (coughs/hour) as measured by LCM reflecting the absolute change from Baseline to Visit 5 and 8 (Week 12 and 24).

The following plot will be produced for cough frequency (coughs/hour) as measured by LCM:

- Mean Cough Frequency (coughs/hour) as measured by LCM Change from Baseline (\pm SD) vs. Visit Week (Week 12, Week 24) with lines for each treatment group.

A linear mixed-effect model (PROC MIXED) will be used and differences between treatment groups between the change from Baseline in coughs/hour as measured by LCM to Weeks 12 and 24 will be examined. Baseline cough frequency (coughs/hour), region, age at screening, sex, baseline D_{LCO} % predicted, and baseline progression-related biomarker (CXCL13, CCL18, MMP3) values each categorized as >Median level vs. \leq Median level will be included as covariates in the model. The model will include a random effect for patient and fixed effects for treatment, visit (Week 12 or Week 24), and the interaction between treatment and visit. To account for correlated repeated measures within patients a compound symmetric variance-covariance matrix will be used.

In order to assess the impact of treatment on cough in those patients for whom coughing is of greatest concern, additional analyses of cough frequency will be performed on the subset of patients with baseline cough severity VAS \geq 40 millimeters and in patients with baseline cough frequency \geq 10 awake time coughs/hour. When examining these subgroups, the outcome will be % change from baseline.

All data for LCM will be presented in a listing.

8.2.2. Change from baseline in the total KBILD score and in the KBILD breathlessness and activity domain score

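### The Week 24 cough recording is worn after Visit 8, so some recordings may be made on a different regimen or off drug, yet SAP 8.2.1 credits them all to the randomised arm

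*Protocol*

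**What the plan says.** **When the monitor is worn.** At Baseline, Protocol 7.2.2 has patients "wear for a 24-hour period prior to coming in for their Baseline visit", so that recording precedes any dose. For the later recordings the same section says: "The LCM and mailing materials will also be dispensed at Visits 5 and 8. Patients will wear for a 24-hour period". The device and diary are then mailed back. The notes to Protocol Tables 5 and 6 say "LCM will be worn for 24 hours at Visits 5 and 8". Neither document gives a maximum delay between Visit 8 and wear. Protocol 7.2.2 leaves further detail on dispensing and return to the clinical study manual.

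**What happens to treatment at Visit 8.** Protocol 6.2.6 lists "Study material dispensation (3-month supply for patients participating in Part B only", and Protocol 8.8.1 has unused ampoules brought back at each visit. Under v2.1 (Synopsis, Study Overview/Design), "all patients who participate in Part B after the implementation of this amendment will be treated with the 100 mg twice daily dose". The same section keeps patients who entered Part B before implementation on their randomised regimen up to that point.

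**How the recording is analysed.** SAP 8.2.1 labels the Visit 8 recording Week 24 and states that "differences between treatment groups between the change from Baseline in coughs/hour as measured by LCM to Weeks 12 and 24 will be examined". The model has fixed effects for treatment, visit and their interaction. Under SAP 5.2 and 5.3 patients are analysed as randomised.

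**The concern.** Visit 8 is the only post-baseline LCM time point at which the plan itself changes or ends treatment. The Week 12 recording also follows its visit, but no regimen change is planned there. A recording labelled Week 24 can therefore reflect the first day or days of Part B treatment, or of no treatment, rather than the end of 24 weeks on the randomised regimen.

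Cough frequency is a listed efficacy outcome, comparing the two regimens is a stated objective (Protocol 2), and Week 24 is the last LCM recording in the trial. The cough-enriched subsets in SAP 8.2.1 use the same recordings in fewer patients, so a few misattributed recordings would weigh more there. The two Week 24 cough measures may also describe different treatments: the cough VAS is completed at the visit and asks about the preceding 2 weeks, whereas the LCM is worn afterwards.

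**Working it through.** There is no figure in the plan to reproduce. Neither document gives a sample size, SD, effect size or power for cough frequency. The check is one of sequence, then of analysis rules, then an illustration of size.

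**1. Sequence at Visit 8 (Day 168 ± 3).** The patient does not hold the device until Visit 8, so the 24 hours must run after dispensing. Three cases follow:

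| Patient | Regimen during the Week 24 recording |
|---|---|
| 100 mg arm, enters Part B | As randomised |
| 50 mg arm, enters Part B before v2.1 is implemented | As randomised, if worn before any later conversion |
| 50 mg arm, enters Part B after v2.1 is implemented | May be 100 mg twice daily |

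A patient of either arm who does not enter Part B receives no supply at Visit 8 and may be recorded off drug.

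**2. Whether an analysis rule catches these recordings.**

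- *Omission of post-switch data:* used for the primary FVC slope (SAP 8.1), the Part B home/clinic correlation (9.1), home FVC (9.2) and the CA19-9/CA-125 correlation (9.4). Not in 8.2.1.
- *Time-varying treatment:* used for in-clinic FVC (8.1), DLCO (8.2.6) and CA19-9/CA-125 (9.4). Not in 8.2.1.
- *Regrouping of switchers (6.1):* applies to Part B summaries, whereas Week 24 is a Part A time point.
- *Per-protocol exclusions (5.3):* a switch required by the amendment is not a study drug deviation, so these recordings stay in.

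**3. How late a recording could count.** For the Part A interim analysis only, SAP 6.4 says "Visit 8 will include data collected up to 36 weeks for HRCT and 28 weeks for all other variables". Week 28 is Day 7 × 28 = 196. From a Visit 8 on Day 165 to 171, that leaves 196 − 165 = 31 down to 196 − 171 = 25 days. This is what the rule would admit, not evidence of what happened.

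**4. Size, switch route.** Let E50 and E100 be the true mean changes, and f the share of 50 mg recordings made on 100 mg twice daily. Assume the full effect of the new regimen is present at once.

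- 50 mg arm mean: (1 − f)E50 + f·E100
- 100 mg arm mean: E100
- Difference: (1 − f)(E100 − E50)

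To show what this means for precision, take 50 per arm and an assumed standardised difference of 0.5. Two-sided 5% power is approximately Φ(0.5(1 − f)√(50/2) − 1.96):

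| f (assumed) | Difference retained | Power |
|---|---|---|
| 0 | 100% | 70.5% |
| 5% | 95% | 66.1% |
| 10% | 90% | 61.4% |
| 20% | 80% | 51.6% |

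**5. Size, off-drug route.** Let q50 and q100 be the off-drug shares, and assume no effect remains off drug. The difference becomes (1 − f − q100)(E100 − E50) + (q50 − q100)E50. With equal shares q this is (1 − f − q)(E100 − E50), a further dilution. With unequal shares the second term can push the estimate either way. The documents give none of f, q50 or q100.

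**The case against.** The strongest reply is that the exposure is narrow. Only 50 mg patients recorded after v2.1 was implemented can have switched. Protocol 1.2.4 says the DSMB acted on preliminary 6-month results, so some patients had already passed Week 24. This stands: f may be small, and it is zero for anyone recorded before implementation.

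A reader might infer that recordings were commonly made weeks late. The documents do not show this. The Week 28 allowance is confined to the Part A interim analysis and covers all variables except HRCT. It would also admit a Visit 8 held late, with the patient still on Part A drug. The Part B calls ask about "status of the LCM return (when applicable", but late return is not late wear, and the Visit 2A call asks about return too, although the baseline device was worn before the visit. The table note ties wear to the visit, and the study manual, which is not among the documents, may fix a date. None of this removes the point: a recording begun soon after Visit 8 can still fall on the new regimen or off drug.

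A reader might also infer that 24-hour cough frequency changes at once with regimen. Protocol 1.2.3 reports cough as the most common Phase 1 event, but it was mild and self-limited after a single dose. Nothing shows that it forms a material share of coughs per hour. Full immediate onset is therefore an assumption; slower onset with prompt wear would mean less dilution.

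Finally, the plan helps in part. The switch date is defined (SAP 6.2.8), listings flag the switch, all LCM data are listed, and the Week 12 contrast is estimated separately. A listing lets a reader find affected recordings, but it does not correct the Week 24 estimate.

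**Conclusion.** The point holds in conditional form. Following the plan as written can credit a post-switch or off-drug recording to the randomised arm at Week 24, and SAP 8.2.1 has neither of the two devices that the SAP uses for the switch elsewhere.

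The size is unknown. Under full immediate onset, the arm difference keeps 95% to 80% of its true size for f = 5% to 20%; those shares are illustrative. Off-drug recordings can add dilution, or bias in either direction if their share differs by arm.

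The documents do not support concluding that the Week 24 contrast as a whole fails to describe the randomised regimens, or that a large part of any effect is lost. That would need counts they do not contain. Cough frequency is a secondary endpoint and SAP 6.1 plans no formal hypothesis tests, so what is at stake is the estimated between-arm difference and the change from baseline. The correction is worth making because it is cheap and brings the cough analysis into line with the others.

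**What to change.** Add to SAP 8.2.1:

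1. Compare each Week 24 LCM wear date with the dosing switch date (SAP 6.2.8) and the last dose date (SAP 6.2.4). Confirm first that the start of recording can be retrieved from the device data or the diary.
2. Omit recordings begun after the switch from the Week 24 between-arm comparison, as is done for spirometry, or keep them and use time-varying treatment as in 8.1 and 8.2.6.
3. Flag recordings begun after the last dose, and show the Week 24 result with and without them.
4. Report the counts per arm, and state the longest delay after Visit 8 at which a recording still counts as Week 24.

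For any patient who has not yet reached Visit 8, and in future protocols, supply the monitor beforehand so that it is worn in the 24 hours before the visit, as at Baseline. SAP 3.0 is dated nine months after protocol v2.1, so this may help few or no patients here, and it would mix pre-visit and post-visit recordings within one time point.

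The cost is a few sentences and a date comparison. Under the omission option, some Week 24 recordings leave the main comparison: a share f of the 50 mg arm's recordings. Excluding off-drug recordings selects on a post-randomisation event, so that exclusion should be a sensitivity analysis, not the main result.

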#### **7.2.3. DLCO**

DLCO will be collected at each visit. For predicted normal values, different sites may use different prediction formulas, based on the method used to measure DLCO. In any case, the method used must be in compliance with the ATS/ERS guidelines on DLCO measurements and the prediction formula appropriate for that method. Raw data (gas mixture, equation used for prediction of normal, further adjustments made if so) must be traced.

#### **7.2.4. Cough Visual Analogue Scale (VAS)**

The Cough VAS will be completed at Baseline, all subsequent visits and the Follow-up visit. This is a paper-based scale that will be completed by the patient at the relevant visits. The results of the scale will be measured in millimeters and entered into the appropriate eCRF. Appendix 17.1 presents an example of the Cough VAS.

Avalyn Pharma, Inc.  
AP01-002

Protocol V2.1  
12 OCT2020

### **7.2.5. The King's Brief Interstitial Lung Disease (KBILD)**

The KBILD Questionnaire will be completed at Baseline, all subsequent visits and the Follow-up visit. This is a paper-based questionnaire that will be completed by the patient at the relevant visits. The results of the KBILD will be entered into the appropriate eCRF. Appendix Section 17.2 presents the KBILD Questionnaire.

